IRB Minimal Risk Protocol Template

Note: If this study establishes a human specimen repository (biobank) for research purposes, do not use this template. Use the Mayo Clinic Human Specimen Repository Protocol Template found on the IRB home page under Forms and Procedures at <http://intranet.mayo.edu/charlie/irb/>

First-time Use: Use this template to describe your study for a new IRB submission.

1. Complete the questions that apply to your study.
2. Save an electronic copy of this protocol for future revisions.
3. When completing your IRBe application, you will be asked to upload this document to the protocol section.

Modification: To modify this document after your study has been approved:

1. Open your study in IRBe. Click on the study 'Documents' tab and select the most recent version of the protocol. Save it to your files.
2. Open the saved document and activate "Track Changes".
3. Revise the protocol template to reflect the modification points, save the template to your files
4. Create an IRBe Modification for the study and upload the revised protocol template.

General Study Information

Principal Investigator: [name], Magnetic Resonance Technology and Use Design Lab, Department of Radiology, Mayo Clinic, Rochester

Other Study Staff: [name],
[name]
[name]

Study Title: **Detection of the occurrence of infiltration of gadolinium injection in brain MR scans using artificial intelligence.**

Protocol version number and date: Version 2: January 20th, 2022

Research Question and Aims

Hypothesis: Machine learning can be used to make a binary decision regarding the occurrence of infiltration of the MR contrast agent, gadolinium, through analysis of MR Brain scan images.

Aims, purpose, or objectives: The aim of this study is to *develop* machine-learning algorithms and infrastructure through the analysis of MR image data for training and testing, for the detection of intravenous infiltration of MR contrast agent. This aim will be achieved through the analysis of both non-infiltrated and infiltrated brain MR images. This analysis will involve segmenting and analyzing the nasal mucosa region following contrast agent administration. The developed machine learning model will be trained to be able to differentiate between non-infiltrated (contrast-enhanced) and infiltrated MR images and thus determine if infiltration has occurred. The training and testing data will include both prospective and retrospective MR data.

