Medical charts will be abstracted for imaging and pathologic findings. Patients will undergo their one additional MR sequence as part of their clinical MRI brain scan. This additional sequence will be included prior to IV contrast administration as part of the standard MR brain without and with IV contrast examination.

Commercially available MRI scanners (General Electric (GE) Medical Systems, Wauwatosa, WI, USA at both 1.5T and 3T and Siemens, Siemens Healthcare, Germany) will be used.

Study Procedure

Commercially available MRI scanners (General Electric (GE) Medical Systems, Wauwatosa, WI, USA at both 1.5T and 3T and Siemens, Siemens Healthcare, Germany at both 1.5T and 3T) will be used. A total of 40 patients will be recruited and randomly selected from the cohort of patients undergoing a MR brain without and with IV contrast examination on the Siemens 1.5T and 3T, and GE 1.5T and 3T MR scanners within the clinic. The additional sequence will be a sagittal T1 CUBE FS for the GE scanners and a sagittal T1 SPACE FS for the Siemens scanners.

The additional sequence will be anonymized and stored for subsequent analysis using the machine learning model as part of the training phase.

This study involves the development of an AI algorithm which analyze images from routine Brain without and with IV contrast agent (Gadolinium (Gd)) examinations to confirm that Gd contrast agent has been correctly administered. The training and testing data will include both prospective and retrospective MR data. We require additional data which simulates the occurrence of IV infiltration during a routine brain without and with IV contrast exam as currently there is a low number of previous studies (n= 50) with associated MR images demonstrating IV infiltration. The data collected as part of this innovation study will be used to augment the retrospective data already collected for the training and testing of the developed AI algorithm.

The machine learning training and testing process is described below and illustrated in Figure 1.

- i. Training Phase - Predictive machine learning models for detection of infiltration will be developed and the performance optimized. Machine Learning Tasks will be to (a) differentiate nasal mucosa with Gd contrast agent uptake vs. nasal mucosa or eye fat ratio without Gd contrast agent uptake.

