- ii. Test Phase - Evaluate the machine learning model and then compare them with the assessment by radiologists using McNemar's test and Receiver Operator Curve (ROC) analysis with specificity threshold equivalent to clinical reporting.

[figure not shown]

Figure 1: (a) Radiomics Machine Learning model development and training workflow. (b) (i) During training, the network weights will be optimized according to the error calculated by the binary loss function; (ii) After each training epoch, the model performance will be assessed by the area under the receiver-operating characteristic curve (AUC) on the validation set; (iii) The parameters of the model predictions will be recalibrated using the unseen calibration dataset and (iv) Model testing will be carried out in the unseen test cohort using the best performing model identified from the validation set and the performance will be evaluated using receiver-operator characteristic curve analysis, net benefit analysis and intra-class correlation coefficient.

Subject Information

Target accrual is the proposed total number of subjects to be included in this study at Mayo Clinic. A "Subject" may include medical records, images, or specimens generated at Mayo Clinic and/or received from external sources.

Target accrual: 40

Subject population (children, adults, groups): Adults undergoing MR brain without and with IV contrast examination as part of their care plan.

Inclusion Criteria:

Patients undergoing a MR brain without and with contrast examination on any GE or Siemens 1.5T and 3T MRI system within Mayo Clinic, Rochester, as part of their care plan.

Exclusion Criteria:

Pregnant Women and individuals under the age of 18 years.

Review of medical records, images, specimens

Check all that apply (data includes medical records, images, specimens).

Only data that exists before the IRB submission date will be collected.

Date Range for Specimens and/or Review of Medical Records:

Note: The Date Range must include the period for collection of baseline data, as well as follow-up data, if applicable.

The study involves data that exist at the time of IRB submission **and** data that will be generated after IRB submission. Include this activity in the Methods section.

Examples

- The study plans to recruit subjects undergoing a MR brain without and with IV contrast examination as part of their care plan.

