The study will use data that have been collected under another IRB protocol. Include in the Methods section and enter the IRB number from which the research material will be obtained. *When appropriate, note when subjects have provided consent for future use of their data and/or specimens as described in this protocol.*

Enter one IRB number per line, add more lines as needed

Data Specimens Data & Specimens _____

Data Specimens Data & Specimens _____

Data Specimens Data & Specimens _____

Data Analysis

Power analyses may not be appropriate if this is a feasibility or pilot study, but end-point analysis plans are always appropriate even if only exploratory. Provide all information requested below, or provide justification if not including all of the information.

Power Statement: Not applicable – pilot study

Data Analysis Plan:

Receiver operating characteristic (ROC) curves will be generated for radiologist diagnosis and the machine learning models decisions and compared using the Delong test. Cut-off values for the machine learning models will be selected to match the sensitivity of radiologist clinical assessment in the training cohort, in order to construct working points of the models that maintain clinically achieved detection rates for the specific clinical exams. The sensitivity and specificity of the machine learning models will be compared based on the reduction of false-positive (FP) decisions compared with the clinical reference. The performance of the machine learning models will be compared to that of the radiologist performance using the McNemar test.

Endpoints

Primary: Area-under-curve performance for each machine learning model and the performance measure “net benefit”. Net benefit is defined as:

$$\text{Net benefit} = \frac{\text{True positives}}{\text{Total number of patients}} - \frac{\text{False positives}}{\text{Total number of patients}} \times w$$

The weighting factor, w , corresponds to the odds (i.e. the harm-to-benefit ratio) of the chosen risk threshold. Retest-repeatability of the model determined from intra-class correlation coefficient (ICC).

Secondary: Sensitivity and specificity of each machine learning model and comparison with radiologist performance using the McNemar test.

References

1. OECD Health Statistics. Health care utilisation. OECD. Stat Web site. Available at: http://stats.oecd.org/Index.aspx?DataSetCode=HEALTH_PROC.

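### Retest ICC in a test cohort holding both classes is raised by class separation and shifts with the infiltrated share; repeatability should be reported by class

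*Protocol*

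**What the plan says.** The primary endpoint paragraph (Data Analysis, Endpoints) names AUC and net benefit, then adds "Retest-repeatability of the model determined from intra-class correlation coefficient (ICC". It gives no form of ICC, no threshold and no split by class.

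The Figure 1 caption (Study Procedure), step (iv), says where the measure is computed: "Model testing will be carried out in the unseen test cohort using the best performing model identified from the validation set". In that cohort "the performance will be evaluated using receiver-operator characteristic curve analysis, net benefit analysis and intra-class correlation coefficient".

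The aims say of the data as a whole: "This aim will be achieved through the analysis of both non-infiltrated and infiltrated brain MR images". The share of infiltrated exams in the test cohort is not stated. On numbers, Study Procedure says that "currently there is a low number of previous studies (n= 50) with associated MR images demonstrating IV infiltration", and the prospective part has "Target accrual: 40".

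**The concern.** An ICC is the variance between exams divided by the total variance. In a cohort holding both classes, scored by a model trained to separate them, part of the between-exam variance is the distance between the class means. That part says how well the model discriminates. It does not say whether the same exam gets the same score twice.

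Two things follow. A score that repeats only moderately within a class can show a good pooled ICC. And the same model with the same measurement error gives different ICCs in cohorts with different infiltrated shares. Here that share depends on how a small set of infiltrated exams is divided among training, validation, calibration and test sets. At stake is a measure listed as primary: a reader could take the ICC as evidence of stable output while a material fraction of infiltrated exams, the ones the tool is meant to catch, change decision on repeat.

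**Working it through.** The protocol gives no ICC value, AUC, class share or reliability, so there is no figure of its own to reproduce. The check is on the mechanism, with assumed inputs shown over a range.

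**Inputs**
- From the protocol: the ICC is computed in the unseen test cohort, next to two measures that need both classes (Figure 1 caption, step iv); cut-offs are chosen to match radiologist sensitivity, whose value is not given (Data Analysis Plan).
- Assumed: normal scores with variance 1 in each class; within-class reliability r (0, 0.5 or 0.9); AUC 0.90, 0.95 or 0.99; infiltrated share p of 50%, 10% or 5%; sensitivity 0.90.

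**Formulas**
- Class separation: d = √2 × z(AUC). This gives d = 1.81, 2.33 and 3.29, so d² = 3.29, 5.41 and 10.82.
- Variance due to class: b = p(1−p)d².
- Pooled ICC = (b + r)/(b + 1). The within-class ICC is r.

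**Within-class reliability 0.5**

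| AUC | b, p = 50% | pooled ICC | b, p = 10% | pooled ICC |
|---|---|---|---|---|
| 0.90 | 0.821 | 1.321/1.821 = 0.73 | 0.296 | 0.796/1.296 = 0.61 |
| 0.95 | 1.353 | 1.853/2.353 = 0.79 | 0.487 | 0.987/1.487 = 0.66 |
| 0.99 | 2.706 | 3.206/3.706 = 0.87 | 0.974 | 1.474/1.974 = 0.75 |

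Every entry exceeds the true within-class value of 0.5, by 0.11 to 0.37. At AUC 0.99 the figure falls further to 0.67 with 5% infiltrated exams, with no change in the model or its error.

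**Zero within-class reliability (class separation alone)**
- AUC 0.99: 0.73, 0.49 and 0.34 at p = 50%, 10% and 5%.
- AUC 0.95: 0.57, 0.33 and 0.20.
- AUC 0.90: 0.45, 0.23 and 0.14.
- To reach 0.75 at p = 50%, d must be 3.46, an AUC of about 0.993.

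A simulation with two repeats and a one-way ANOVA ICC agreed with the formula on the raw score. On a calibrated probability score the zero-reliability values at p = 50% are higher: 0.49, 0.65 and 0.85 at AUC 0.90, 0.95 and 0.99.

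**Change of decision on repeat, infiltrated exams**
- With sensitivity fixed at s and r = 0, the rate is 2s(1−s) whatever the AUC: 2 × 0.90 × 0.10 = 18%.
- With r = 0.5, the bivariate normal gives 13.5% at s = 0.90.

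So at AUC 0.99 and p = 50%, a pooled ICC of 0.87 can sit beside 13.5% of infiltrated exams changing decision.

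**The case against.** **Pooling is inferred.** The protocol nowhere says that the classes are combined, and the form and stratification of an ICC are often left to an analysis plan, which is not at hand. This stands as a limit on the claim. But the protocol itself fixes the statistic, ranks it with the primary endpoints and names the cohort. Followed as written, those three choices lead to the pooled value.

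**A reader might infer that class separation alone yields a high ICC, so that a wholly unrepeatable score would pass.** The figures do not support that in general. With zero reliability on the raw score, a high value needs near-perfect discrimination; at AUC 0.90 it is 0.45 or less, which would expose the problem.

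**A reader might also infer that the pooled ICC merely restates AUC and case mix.** It does not. At AUC 0.95 and 10% infiltrated exams it is 0.33, 0.66 and 0.93 for reliability 0, 0.5 and 0.9. It tracks repeatability, but from a raised and moving baseline.

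**Most decisions are stable when discrimination is strong.** At AUC 0.99, sensitivity 0.90 and zero reliability, specificity is 0.978, so 2 × 0.978 × 0.022, about 4.4%, of non-infiltrated exams change. Overall change is about 11% at 50% infiltrated exams and 5.7% at 10%. This is correct, and it is why the rate should be given in each class: the overall figure hides the infiltrated exams. The sensitivity of 0.90 is an assumption.

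**A pooled ICC is legitimate for a population holding both classes, and this pilot sets no ICC threshold.** Both points stand. The pooled value need not be dropped, and no stated decision rule is invalidated.

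**Repeats are not described.** Study Procedure and Methods provide one added sequence per prospective patient ("Patients will undergo their one additional MR sequence as part of their clinical MRI brain scan") and say nothing of a repeat. That is a separate matter. Supplying repeats would not remove the inflation, and by-class reporting needs repeats just as the pooled ICC does.

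**Conclusion.** The point holds in moderate form. On the natural reading of the endpoint text and the Figure 1 caption, the retest ICC mixes both classes, and its value is then inflated by discrimination and dependent on an unstated infiltrated share. With within-class reliability 0.5 the inflation is 0.23 to 0.37 at 50% infiltrated exams and 0.11 to 0.25 at 10%, over AUC 0.90 to 0.99. This rests on equal-variance normal scores and on assumed AUC, reliability, case mix and sensitivity; the protocol gives none of these. The documents do not show that pooling is prescribed, that the pooled ICC is uninformative, or that an unrepeatable score would generally look repeatable. This is a worthwhile, cheap improvement to an endpoint listed as primary, not a fatal flaw.

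**What to change.** In the primary endpoint text, state that repeatability is reported separately for infiltrated and non-infiltrated test exams, as the within-class ICC and the within-exam SD of the score. Add the percentage of exams in each class whose yes/no decision changes between repeats at the chosen working point. If a pooled ICC is also shown, present it as a supplement and give the class mix beside it.

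This is a short addition to the endpoint text. It needs no repeats beyond those the endpoint already requires. The price is precision and appearance: the ICC for infiltrated exams will have a wider interval, because at most a part of the 50 existing infiltrated studies can fall in the test cohort, and it will look less favourable than the pooled value.
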